From recent meta-analysis, three dual-armed studies that compared embolization and conventional surgery groups and six single-armed case series were identified and analyzed. Hematoma recurrence rate was significantly lower in the embolization group compared to the conventional treatment group (2.1% vs 27.7%, OR .087, 95% CI .026-.292, $p<.001$, $I^2=0\%$), whereas surgical complication rates were similar between the two (2.1% vs 4.4%, OR 0.563, 95% CI 0.107-2.96, $p=.497$, $I^2=27.5\%$). Number of patients with mRS>2 in the embolization (12.5%) versus conventional treatment (9.1%) groups also showed no statistical difference ($p=.689$). A composite hematoma recurrence rate of 3.6% was found after summing the six-case series. Composite recurrence and complication rates in the embolization cohorts of the dual-armed studies as well as the case series were also lower than literature values for conventional surgical treatments. Since then, there has been one study with 60 embolizations showing a 90% success rate of avoiding subsequent surgery with no procedural-related complications.

Objective

Through the use of a prospective dual cohort, this study seeks to assess the safety and efficacy of middle meningeal artery embolization for subdural hematoma in addition to standard treatments, which include observation and surgical evacuation. Middle meningeal artery embolization has emerged recently as a minimally invasive and successful method of preventing re-accumulation of subdural hematoma, particularly for patients that are not obvious surgical candidates or those with recurrent or refractory hematomas. We will compare the outcomes of these two groups of patients who undergo middle meningeal artery embolization to matched historical controls from the past four years.

Specific Aim 1:

Determine the efficacy of middle meningeal artery embolization vs observation alone

The recurrence rate of patients that undergo the middle meningeal artery procedure will be compared to a number of medically managed patients that experience a clinically significant persistent or recurrent hematoma. This endpoint will be determined through a series of neurologic assessments and follow up imaging. Patients will be followed for 90 days.

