information gathered, time frame of participation, potential benefits, and risks of participation, including the risks of undergoing an interventional neuroradiology procedure. Treatment with middle meningeal artery embolization will be offered in addition to the standard surgical evacuation or observation by the physician in consideration of the patient's medical history and current condition. If patients are unable to provide informed consent, consent from the next of kin will be obtained in accordance with Missouri Statute Title XXVII, Section 431.064.

Patients will have as much time as they desire to think about the study, ask questions, and discuss with family. Any patient requiring emergent intervention or experiencing sudden neurologic deterioration is excluded from this study. The consent documentation contains a statement that consent is freely given, that the patient understands the potential risks and benefits of entering the study, and that the patient is free to withdraw from the study at any time. As the patient may experience a direct benefit from the study, the patient must initial yes/no to permission for future use of their data per policy. Patients who agree will then sign the IRB approved consent form prior to undergoing the procedure. The original signed consent will be maintained in a binder in a locked office. A copy will be given to the patient, with contact numbers if the patient has further questions or wishes to withdraw their consent. The expected duration of patient participation in the study is 90 days.

Based on a review of prior literature, we expect an effect size of 20% patients to meet the endpoint of recurrent or refractory subdural hematoma requiring surgery. With the addition of MMA embolization, we expect that only 5% of patients will meet this outcome. With equal numbers of patients in each arm, we estimate that 124 patients will be needed for a power of 80% using a two tailed alpha set at 0.5. In order to account for study dropout, we plan to study 200 patients who undergo MMA embolization. These patients will be compared to an additional 400 historical matched controls obtained via retrospective chart review from January 1st 2014 to December 31st 2018.

Inclusion/Exclusion Criteria

Must meet the following criteria for inclusion to undergo MMA embolization:

1. Patients 18 years or older undergoing treatment for a new diagnosis of chronic or acute subdural hematoma (cSDH)
or

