The National Institutes of Health Stroke Scale (NIHSS) is an objective measure of impairment caused by a stroke. Eleven items are evaluated, with a potential score ranging from 0 to 42, with a higher score indicating more impairment.

Privacy/Data Protection

Patients will be assigned a unique study identification number at the time of consent. This number will link to identifying protected health information in a separate locked database accessible only to relevant research team members. Clinical study data will be entered into a secure database on RedCap under the study ID number to maintain patient data confidentiality.

Screening:

Study ID	MRN	Last Name	First Name	Admit Date	Enrolled Y/N	Date Consent Signed	Signed By Patient/ LAR	Exclusion

Initial Data:

Study ID	Birth Year	Sex	Race	(relevant comorbidities)	Use Anticoagulant y/n	Name of Med (aspirin, warfarin)	Procedure Date	Presenting neuro symptoms

Any neuro history	NIHSS Presentation	Baseline mRS	Size of SDH at Presentation	Laterality of SDH Left Right bilateral	Procedural Complications	

Follow up:

Study ID	Date of Follow Up	Time Point (30, 90 days)	NIHSS	mRS	Size of SDH at follow up	Neuro Deficit

Analysis

Endpoints

Two primary endpoints will be analyzed, related to the two main aims of the study. Aim 1 is to establish if middle meningeal artery embolization is more effective than observation alone at preventing recurrence of subdural hematoma. Aim 2 is to determine if adding on middle meningeal artery embolization reduces the need for further surgery in patients that initially undergo evacuation. The number of patients that experience a recurrent or refractory subdural hematoma will be compared, as well as the number of patients in each group that require surgery after undergoing embolization.

Primary Endpoints:

Recurrent or progressive SDH
Secondary surgical evacuation required

Secondary Endpoints:

Change in size of SDH at follow up
Procedure-related complications
New neuro deficit
NIHSS/mRS at follow-up intervals

Statistical Analysis

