Based on a review of prior literature, we expect an effect size of 20% of patients to meet the endpoint of recurrent or refractory subdural hematoma requiring surgery. With the addition of MMA embolization, we expect that only 5% of patients will meet this outcome. With equal numbers of patients in each arm, we estimate that 124 patients will be needed for a power of 80% using a two tailed alpha set at 0.5. In order to account for study dropout, we plan to study 200 patients who undergo MMA embolization.

This study will be stopped prior to its completion if: (1) the intervention is associated with adverse effects that call into question the safety of the intervention; (2) difficulty in study recruitment or retention will significantly impact the ability to evaluate the study endpoints; (3) any new information becomes available during the trial that necessitates stopping the trial; or (4) other situations occur that might warrant stopping the trial.

References

1. Ban, S. P., Hwang, G., Byoun, H. S., Kim, T., Lee, S. U., Bang, J. S., Oh, C. W. (2018). Middle Meningeal Artery Embolization for Chronic Subdural Hematoma. *Radiology*, 286(3), 992-999. doi:10.1148/radiol.2017170053
5. Fiorella, D., & Arthur, A. S. (2019). Middle meningeal artery embolization for the management of chronic subdural hematoma. *J Neurointerv Surg*. doi:10.1136/neurintsurg-2019-014730

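### The 80% power is calculated for one equal-arm comparison, but the study makes two comparisons and sets no minimum cohort size, so 80% is not assured for any particular aim

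*Combined protocol and SAP*

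**What the plan says.** The sample-size paragraph under Methodology, Participants gives one calculation. For controls, "we expect an effect size of 20% patients to meet the endpoint of recurrent or refractory subdural hematoma requiring surgery". For the treated arm, "With the addition of MMA embolization, we expect that only 5% of patients will meet this outcome". Then: "With equal numbers of patients in each arm, we estimate that 124 patients will be needed for a power of 80" per cent, "using a two tailed alpha set at 0.5". The enrolment target follows: "In order to account for study dropout, we plan to study 200 patients who undergo MMA embolization". The control group is given as one total: "These patients will be compared to an additional 400 historical matched controls". Safety and Analysis repeats the calculation and the 200, but not the 400.

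The design elsewhere has two parts. The Groups list defines two embolization cohorts (embolization only; embolization plus standard evacuation) and two historical cohorts (medical management; surgery alone). Specific Aims 1 and 2 give each embolization cohort its own population and comparator. The Endpoints section confirms it: "Two primary endpoints will be analyzed, related to the two main aims of the study".

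No section gives a target or minimum for either embolization cohort, a division of the 400 controls, power for either aim, or a dropout rate.

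**The concern.** The 80% describes a comparison that the study does not make. Each aim will be tested on its own share of the 200 embolized patients, and the plan leaves that share to whoever happens to enrol. Recruitment could close at 200 with one cohort well short of the number it needs, and nothing in the plan would flag it; the stopping criteria in Safety and Analysis contain no threshold by cohort. A null result in that cohort could then be read, against a stated 80% power, as evidence that embolization does not help that population.

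There is also a gap by endpoint. The 20% and 5% are rates of haematoma requiring surgery. Specific Aim 1 leads with recurrence or persistence and compares the need for surgery only secondarily. The plan gives no assumed rates for recurrent or progressive SDH, so its power on that primary endpoint is unknown.

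**Working it through.** **Inputs from the plan.** Control rate 0.20, embolized rate 0.05, two-tailed test, 200 embolized, 400 controls.

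**Assumptions.** Alpha is 0.05 (0.5 is printed in both places). Each aim has two controls per embolized patient, inferred from the totals 200:400; the plan does not state a ratio by aim. Matching and any bias from historical controls are ignored.

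**Formula** (pooled two-proportion z-test, n1 embolized, n2 controls):
- p̄ = (n1·0.05 + n2·0.20)/(n1 + n2)
- SE0 = √[p̄(1 − p̄)(1/n1 + 1/n2)]
- SE1 = √[0.05·0.95/n1 + 0.20·0.80/n2]
- power = Φ[(0.15 − 1.96·SE0)/SE1]

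**1. The plan's own figure, equal arms.** Here p̄ = 0.125.
- 124 as a total (62 per arm): SE0 = 0.0594, SE1 = 0.0579, (0.15 − 0.1164)/0.0579 = 0.58, power 72%.
- 124 per arm: power 95%.
- Smallest design reaching 80%: 76 per arm, 152 in total.
- Alpha taken literally as 0.5: 22 per arm, 44 in total.
- Nearest match: a one-sided 0.05 test, which gives 81.7% at 62 per arm; the text says two-tailed.

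So 124 is not reproduced from its stated inputs.

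**2. Power for one aim at 1:2.** Here p̄ = 0.15. For 60 and 120: SE0 = 0.0565, SE1 = 0.0461, (0.15 − 0.1107)/0.0461 = 0.85, power 80.3%.

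| Evaluable embolized | Controls | Power |
|---|---|---|
| 20 | 40 | 30% |
| 30 | 60 | 46% |
| 40 | 80 | 60% |
| 50 | 100 | 72% |
| 60 | 120 | 80% |
| 100 | 200 | 96% |
| 140 | 280 | 99.5% |

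**3. Splits of the 200, before dropout.** The larger cohort has at least 100 patients, so at least 96%. At 100/100 both aims have 96%. At 60/140 they have 80% and 99.5%. At 40/160 they have 60% and 99.8%. An aim falls short only when its cohort is below 60, which is 30% of the 200.

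**4. Dropout.** Enrolment needed for 60 evaluable: 60/0.9 = 66.7, so 67 at 10% loss; 60/0.8 = 75 at 20% loss. Two cohorts need 134 or 150, both within 200. The plan's step from 124 to 200 would imply a loss of 1 − 124/200 = 38% if 124 is per arm, or 1 − 62/200 = 69% if it is the total. It states neither.

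**5. Sensitivity.**
- 200 controls for each aim whatever the cohort size: 40 embolized gives 68%, and the minimum becomes 52.
- Alpha 0.025 per aim: the minimum becomes 73 plus 146.
- Embolized rate 10% (from the 60-embolization series in Prior Research, "showing a 90% success rate of avoiding subsequent surgery") against 20%: 39% power at 60/120 and 60% at 100/200; 155 plus 310 would be needed.

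**The case against.** The strongest defence is that 200 plus 400 is generous. On the plan's rates it covers both aims over a wide range of splits, one aim always exceeds 80% before dropout, and enrolling above a calculated minimum is conservative. All of that stands, and it limits the point to the smaller cohort.

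A reader might infer several stronger things that the documents do not support:

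- **That both aims are underpowered.** Before dropout they cannot both be, on these rates: the larger cohort has at least 96%.
- **That departing from equal arms costs power.** It adds power: 60 embolized patients give 70.5% against 60 controls and 80.3% against 120.
- **That the post-surgery cohort will be the small one.** The plan gives no share of patients operated on. It also admits patients with significant residual haematoma or with failed surgery at any point, and it describes evacuation followed by embolization in the same hospitalization. The cohort's size cannot be predicted from the text.
- **That 5% is too optimistic.** Prior Research also reports embolized recurrence of 2.1% and 3.6%, so 5% lies between those and 10%, and it gives 27.7% recurrence under conventional treatment. With 10% against 27.7%, 60/120 has 81% power. Recurrence and surgery are different endpoints, so no pairing is clean, and 10% serves only as one sensitivity value.

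None of this supplies the missing minimum, control split or dropout rate.

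**Conclusion.** The point holds in a limited form. The plan's single power statement belongs to neither named aim, and nothing in the plan guarantees 80% for either one. For the surgery endpoint, the smaller cohort needs 60 evaluable embolized patients; at 50, 40 and 20 its power is 72%, 60% and 30%. This rests on two-sided alpha 0.05 for each aim, an inferred 1:2 ratio, 20% against 5% in both populations, and a z-test. The threshold moves modestly with the number of controls and with any division of alpha, and considerably if the embolized rate is nearer 10%.

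It would be wrong to conclude that the study is too small overall or that a shortfall is expected; the documents show only that one is possible and would go unnoticed. For recurrent or progressive SDH no power can be calculated, because no rates are given. The 124 should not be carried forward as a base for anything.

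**What to change.** Replace the sample-size paragraph under Participants, and its repeat under Safety and Analysis, with a power statement for each aim and endpoint:

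- Correct alpha to 0.05 and drop the 124.
- For the surgery endpoint, state that each aim needs at least 60 evaluable embolized patients and 120 controls for 80% power at 20% against 5%.
- State one dropout rate and the enrolment minimum it implies: 67 per cohort at 10% loss, or 75 at 20%, within the same 200.
- Divide the 400 controls between the two historical cohorts in proportion to the embolization cohorts.
- State separately the rates assumed for recurrent or progressive SDH in each aim, with the resulting power.
- Show a 10% embolized rate as one sensitivity value.
- Report any aim whose cohort misses its minimum as estimation only, with its actual power.

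The minimum need not become a cap. Closing the larger cohort early could slow the study considerably and is not required.

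The cost is rewriting, with no extra patients for the surgery endpoint on the plan's rates. The power shown for the smaller cohort may look less favourable than the present 80%, and the recurrence endpoint may need its own number once its rates are set.

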Statistical comparisons will be made for the number of patients that experience a recurrent or refractory subdural hematoma, as well as the number of patients in each group that require evacuation surgery after undergoing embolization, an indication that the embolization procedure failed. These primary endpoints will be compared with simple t-test. The secondary endpoint of the change in the size of the subdural hematoma on radiographic imaging will be analyzed by repeated measures ANOVA. Change in score on NIH Stroke Scale pre and post embolization will be compared to determine the functional outcome of the procedure. For a safety analysis, the rate of procedure-related complications between embolized patients and surgical controls will be compared by t-test. Rankin Score at the follow up intervals will be compared with a Chi Square analysis.

Safety Monitoring Plan

Research will be performed according to protocols approved by the Institutional Review Board at Washington University in St. Louis School of Medicine. An application to the IRB is currently pending.

Patients with subdural hematoma present with symptoms including confusion or altered mental status, decreased consciousness, weakness or numbness on one side of the body, headache, seizure, and difficulty with speech, swallowing, or walking.

During this study, assessment of medical history and physical examination will be performed at baseline and at stated follow up intervals to ascertain neurologic status, change in functional baseline, and occurrence of any AEs. Prior to interventional procedures, patients have coagulation tests performed to assess risk of bleeding. If the patient has an allergy to iodinated contrast, they will receive standard pre-medication. During the embolization procedure, patients undergo continuous vital sign monitoring and are assessed frequently by a dedicated, ACLS-certified procedural nurse. The patient will be monitored as an inpatient in the neuroICU or stepdown unit for a minimum of 24-48 hours after the procedure.

Adverse Events

An adverse event (AE) is any untoward medical occurrence in a subject during participation in the clinical study or with use of the experimental agent being studied. An adverse finding can include a sign, symptom, abnormal assessment (laboratory test value, vital signs, electrocardiogram finding, etc.), or any combination of these.

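### The plan's only significance level is printed as a two-tailed alpha of 0.5, and its 124 patients cannot be reproduced from the stated inputs at 0.5 or at 0.05

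*Combined protocol and SAP*

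**What the plan says.** The sample-size paragraph under Methodology, Participants, takes 20% of patients reaching recurrent or refractory hematoma requiring surgery, then adds: "With the addition of MMA embolization, we expect that only 5% of patients will meet this outcome". The calculation is made "With equal numbers of patients in each arm", and the result is that "we estimate that 124 patients will be needed for a power of 80% using a two tailed alpha set at 0.5". The Safety and Analysis section repeats the statement with the same alpha: "124 patients will be needed for a power of 80% using a two tailed alpha set at 0.5".

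The planned size is larger than the calculated one. For the embolized patients: "In order to account for study dropout, we plan to study 200 patients who undergo MMA embolization". For the controls: "These patients will be compared to an additional 400 historical matched controls obtained via retrospective chart review". No dropout rate is given.

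The Statistical Analysis section says "These primary endpoints will be compared with simple t-test", and for safety that "the rate of procedure-related complications between embolized patients and surgical controls will be compared by t-test". It also names repeated measures ANOVA and a chi-square test. It gives no significance level for any of them. The Endpoints section lists two primary endpoints, tied to two aims.

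**The concern.** Two things look wrong. First, an alpha of 0.5 read literally accepts a 50% false-positive rate. Nothing elsewhere in the plan overrides it: the p-values and confidence intervals under Prior Research are results of a cited meta-analysis, not criteria for this study. The rule for calling a primary endpoint positive is therefore not validly set in advance. If it is corrected only after the data are seen, the level and its sidedness become post hoc choices, in a comparison that already rests on historical controls.

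Second, if 0.5 were only a typing error, putting 0.05 in its place should return 124. It does not, so the 80% power claim has no traceable basis.

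**Working it through.** **Inputs** (Methodology, Participants): control rate p1 = 0.20; embolization rate p2 = 0.05; equal arms; power 80%; two-tailed alpha 0.5 as printed. The plan calls the 20% an effect size; I read it as the event rate without embolization. The formula and the meaning of 124 (total or per arm) are not stated.

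Difference d = 0.15, so d² = 0.0225. Mean rate 0.125, so 2 × 0.125 × 0.875 = 0.21875 (square root 0.4677). Also 0.20 × 0.80 + 0.05 × 0.95 = 0.2075 (square root 0.4555). For 80% power, z = 0.8416.

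**Step 1. The plan's figure, alpha 0.5 as printed** (z = 0.6745). Pooled two-proportion z-test, per arm:

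n = (z_alpha × 0.4677 + z_power × 0.4555)² / d² = (0.3155 + 0.3834)² / 0.0225 = 21.7, so 22 per arm and 44 in total. Not 124.

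**Step 2. The same with alpha 0.05** (z = 1.9600).

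n = (0.9167 + 0.3834)² / 0.0225 = 75.1, so 76 per arm and 152 in total. Not 124.

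**Step 3. Other independent-group methods.** Unpooled: (z_alpha + z_power)² × 0.2075 / d². Pooled variance in both terms: (z_alpha + z_power)² × 0.21875 / d². Arcsine: 2(z_alpha + z_power)² / h², with h = 2 arcsin√0.20 − 2 arcsin√0.05 = 0.4763. Continuity-corrected: (n/4)(1 + √(1 + 4/(nd)))², with n the pooled result before rounding.

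| Method | Two-sided 0.05: per arm (total) | Two-sided 0.5: per arm (total) |
|---|---|---|
| Pooled | 75.1 → 76 (152) | 21.7 → 22 (44) |
| Unpooled | 72.4 → 73 (146) | 21.2 → 22 (44) |
| Pooled in both terms | 76.3 → 77 (154) | 22.3 → 23 (46) |
| Arcsine | 69.2 → 70 (140) | 20.3 → 21 (42) |
| Continuity-corrected | 87.9 → 88 (176) | 33.7 → 34 (68) |

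Neither 124 in total nor 124 per arm lies in either column's range.

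**Step 4. Power that 124 gives.** Power = Φ((d − z_alpha × s0) / s1), with s0 = 0.4677/√n and s1 = 0.4555/√n, n per arm.

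- 124 as a total (62 per arm), alpha 0.05: (0.15 − 1.96 × 0.0594) / 0.0579 = 0.58, power 71.9%.
- 124 per arm, alpha 0.05: (0.15 − 1.96 × 0.0420) / 0.0409 = 1.65, power 95.1%.
- At alpha 0.5: 97.1% and 99.9%.

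No combination gives 80%.

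**Step 5. Where 124 might have come from.** One-sided 0.05 at 80% power gives 120 (pooled) or 122 (pooled in both terms) in total. Two-sided 0.05 at 95% power gives 123.4, so 124 per arm. The first contradicts the stated two tails and the second the stated 80%. The origin cannot be determined.

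**Step 6. Power by aim.** The plan gives no split of the 200 between aims. Assuming two controls per embolized patient and the same rates, the mean rate is (0.05 + 2 × 0.20)/3 = 0.15. With n embolized and 2n controls, s0 = √(0.1275 × 1.5/n) and s1 = √(0.0475/n + 0.16/(2n)). At two-sided 0.05:

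| Embolized vs controls | Power |
|---|---|
| 100 vs 200 | 96% |
| 60 vs 120 | 80% |
| 50 vs 100 | 72% |
| 40 vs 80 | 60% |

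**The case against.** The strongest reply is that this is one typing error, copied with its paragraph, that nobody would apply literally, and that the planned 200 embolized patients exceed 124 on either reading. Much of that is fair. The second occurrence is not independent evidence, and the 50% false-positive rate describes a reading the authors almost certainly did not intend. But the reply does not supply the missing threshold in the Statistical Analysis section, and correcting the slip does not make 124 right.

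A second reply is that the controls are described as matched, so independent-group formulas may not apply. A McNemar calculation at two-sided 0.05 does give about 62 pairs (124 patients) if the discordant proportion is assumed to be about 0.185. The plan states no such input and does not name a paired test, so this does not recover the figure. It does mean that the ranges above should be read as independent-group ranges.

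Three stronger readings are tempting and not supported. A reader might infer that the study is underpowered; the plan's numbers do not show that. A reader might infer the opposite, that 200 against 400 makes power a non-issue; but the plan defines no single pooled comparison. It has two aims, two embolization groups and two historical cohorts, and an uneven split could leave one aim below 80%. A reader might also turn alpha into a fixed count of events needed for success. That count depends on the test: in a pooled illustration, 27/200 against 80/400 gives p = 0.0499 by z-test and 0.05002 by pooled-variance t-test.

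**Conclusion.** The point holds. The only significance level set for the trial's own tests is invalid as printed, and the stated sample size does not follow from its inputs at two-sided 0.5 or 0.05. At 0.05 the total should be 152 by the pooled z-test (140 to 176 across methods) against the stated 124, and power at 124 is 72% or 95%, not 80%. These figures assume independent groups, 1:1 allocation and the plan's rates of 20% and 5%.

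The conclusion stops there. That 0.05 was intended is very likely but not stated. Adequate power for each aim is neither shown nor refuted: the 60% to 96% range above rests on assumed splits and an assumed 1:2 control ratio.

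**What to change.** 1. In both sample-size paragraphs (Participants; Safety and Analysis), replace the alpha of 0.5 with two-sided 0.05, the authors confirming that this level and sidedness were intended.
2. In Statistical Analysis, state that this is the analysis threshold, and whether it applies to each of the two primary endpoints or is shared between them.
3. Either replace 124 with a reproducible figure that names its formula and says total or per arm, for example 152 in total (76 per arm) by the pooled two-proportion z-test without continuity correction; or drop 124 and give the power for each aim's own comparison under a stated split of the 200 embolized patients and their controls.

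The cost is a wording change in two paragraphs, a sentence or two in Statistical Analysis and one recalculation. The correction itself asks for no new patients, visits or data.
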